### **3.4 Explanation for choice of comparator (or placebo)**

Since the efficacy of the pudendal nerve block in patient operated for hemorrhoidectomy under spinal anaesthesia is not well established, the purpose is to evaluate differences in the postoperative pain if the nerve block is performed or not.

### **3.5 Risks / Benefits**

The risks related to the pudendal nerve block are extremely rare. Complications include the intravenous injection of the anaesthetic, the formation of a retroperitoneal hematoma or abscess of the psoas muscle. In case such complications occur, a multidisciplinary team composed by anaesthesiologist, surgeons and interventional radiologist will be promptly available.

### **3.6 Justification of choice of study population**

Patients affected by haemorrhoids (grade III and IV) and treated with Milligan-Morgan hemorrhoidectomy

## **4. STUDY OBJECTIVES**

### **4.1 Overall Objective**

The purpose is to evaluate differences in the postoperative pain if the pudendal nerve block is performed or not in patients treated for hemorrhoidectomy under spinal anaesthesia.

### **4.2 Primary Objective**

Postoperative pain evaluation

### **4.3 Secondary Objectives**

Antalgic drugs as needed (opioids needed)

Length of hospital stay

### **4.4 Safety Objectives**

The safety of the pudendal nerve block will be assessed. The assessment will be evaluated recording complications (type and severity according to CTCAE Version 4.03 - June 14, 2010^12) after the nerve block during the hospital stay. In-patients will be then controlled 1 months after the operation, out-patients after 1 and 4 weeks.

## **5. STUDY OUTCOMES**

### **5.1 Primary Outcome**

Postoperative pain measured on VAS scale at 6, 12, 24, 48 hours

### **5.2 Secondary Outcomes**

Antalgic drugs as needed (type of drug and number of administrations)

Length of hospital stay (days)

### **5.3 Safety Outcomes**

The type and the severity of AEs related to the pudendal nerve block will be recorded according to CTCAE Version 4.03 - June 14, 2010^12. The evaluation will be done after the nerve block, during the hospital stay and 1 months after the operation for in-patients or after 1 and 4 weeks for out-patients.

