## 10. SAFETY

### 10.1 Drug studies

During the entire duration of the study, all adverse events (AE) and all serious adverse events (SAEs) are collected, fully investigated and documented in source documents and case report forms (CRF). Study duration encompassed the time from when the participant signs the informed consent until the last protocol-specific procedure has been completed, including a safety follow-up period. For adverse event the information collected are: time of onset, duration, resolution, action to be taken, assessment of intensity, relationship with study treatment. The evaluations will be done during the hospital stay and the further planned clinical evaluations.

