#### 10.1.1 Definition and assessment of (serious) adverse events and other safety related events

An Adverse Event (AE) is any untoward medical occurrence in a patient or a clinical investigation participant administered a pharmaceutical product and which does not necessarily have a causal relationship with the study procedure. An AE can therefore be any unfavourable and unintended sign (including an abnormal laboratory finding), symptom, or disease temporally associated with the use of a medicinal (investigational) product, whether or not related to the medicinal (investigational) product.

A Serious Adverse Event (SAE) is classified as any untoward medical occurrence that:

- results in death,
- is life-threatening,
- requires in-patient hospitalization or prolongation of existing hospitalisation,
- results in persistent or significant disability/incapacity, or
- is a congenital anomaly/birth defect.

In addition, important medical events that may not be immediately life-threatening or result in death, or require hospitalisation, but may jeopardise the patient or may require intervention to prevent one of the other outcomes listed above should also usually be considered serious.

SAEs will be followed until stabilisation. Participants with ongoing SAEs at study termination (including safety visit) will be further followed up until stabilisation of the disease after termination.

The Principal Investigator will be informed on the randomization and will be available 24/24 hours, 365 days/year in case of complications related to the pudendal nerve block occur.

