#### Assessment of Causality

The Sponsor-investigator make a causality assessment of the event to the study drug, based on the criteria listed in the ICH E2A guidelines:

Relationship	Description
Definitely	Temporal relationship Improvement after dechallenge* Recurrence after rechallenge (or other proof of drug cause)
Probably	Temporal relationship Improvement after dechallenge No other cause evident

Possibly	Temporal relationship Other cause possible
Unlikely	Any assessable reaction that does not fulfil the above conditions
Not related	Causal relationship can be ruled out
*Improvement after dechallenge only taken into consideration, if applicable to reaction	

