#### **11.3.3 Safety analysis**

The analysis of the safety will be conducted at the end of the study by [name] [name], OBV (Chief of the EOC Biostatistic Service). Parameters analysed will be the type and severity of AEs, treatment and resolution or stabilization (according to CTCAE Version 4.03 - June 14, 2010^12).

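### The safety outcome is defined as block-related AEs, which only Group A can have, while all AEs are collected and the safety analysis does not say which set it uses

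*Combined protocol and SAP*

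**What the plan says.** **Outcome.** Section 5.3 (Safety Outcomes) reads "The type and the severity of AEs related to the pudendal nerve block will be recorded", and section 9.2.3 uses the same restriction. Section 4.4 frames the objective as the safety of the block, assessed by recording complications that follow it. The synopsis lists safety of the block among the secondary outcomes.

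**Collection.** Section 10.1 says that "all adverse events (AE) and all serious adverse events (SAEs) are collected". The period is wide: "Study duration encompassed the time from when the participant signs the informed consent until the last protocol-specific procedure has been completed". Section 10.1.1 defines an AE "whether or not related to the medicinal (investigational) product". Sections 9.2.3.1 and 10.1 list relationship to study treatment among the items recorded for each event.

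**Attribution.** Under Assessment of Causality: "The Sponsor-investigator make a causality assessment of the event to the study drug". Section 1.2 says that sponsor and Principal Investigator are one person. Section 6.3 says that the Principal Investigator is told the allocation.

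**Comparator.** Section 8.2.2 gives Group B no block. No sham procedure is described.

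**Analysis.** Section 11.3.3 states "Parameters analysed will be the type and severity of AEs", together with treatment and resolution or stabilisation. It does not say related or all, and it does not mention arms. Section 11.3 has a general rule that qualitative data are compared between groups by Chi-square or Fisher's exact test.

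**The concern.** An event related to the block needs a block. As sections 5.3 and 9.2.3 are worded, the outcome can therefore be above zero in one arm only. Its value in that arm depends on how an unblinded person classifies ordinary postoperative events. The causality table gives limited protection, since its *possibly* grade needs only a temporal relationship with another cause still possible. Many early events after surgery could meet that.

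At stake is what randomisation can contribute to the safety objective. A count of attributed events in Group A cannot separate what the block adds from what hemorrhoidectomy under spinal anaesthesia produces anyway. Set against a structural zero, it could make the block look harmful. If nothing is attributed, it could look clean without any control rate to read it against.

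**Working it through.** **Step 1. The sections side by side.**

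| Section | Which AEs | Which arms |
|---|---|---|
| 5.3, 9.2.3 (outcome) | related to the block | Group A only, by definition |
| 10.1, 10.1.1, 9.2.3.1 (collection) | all, relationship recorded as a field | both |
| 11.3.3 (analysis) | not specified | not specified |

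The outcome and the collection rule describe different sets of events, and the analysis section does not choose between them.

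**Step 2. Group size.** The plan gives no expected AE rate, so the only figure to reproduce is the sample size in 11.2: 18 / (1 − 0.10) = 20 per group. This agrees with the plan.

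**Step 3. What a structural zero does under the general rule in 11.3.** With x attributed patients in Group A and 0 in Group B, 20 per arm, the two-sided Fisher p-value is 2 × C(20, x) / C(40, x).

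- x = 4: 2 × 4,845 / 91,390 = 0.106
- x = 5: 2 × 15,504 / 658,008 = 0.047

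Five attributed patients are enough. With 18 per arm the threshold is also 5 (p = 0.045). Section 6.1 mentions 100 patients, which does not match 11.2 and is a separate point. At 50 per arm, 5 versus 0 gives 0.056 and 6 versus 0 gives 0.027.

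**Step 4. How often this happens when the block causes nothing.** Assumptions, none of them from the documents: the true all-cause AE rate is the same in both arms, and a fixed share of Group A's events is attributed to the block. The chance of p < 0.05 is P(X ≥ 5) with X ~ Binomial(20, rate × share). The last column counts all AEs in both arms and applies Fisher's test.

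| Assumed AE rate | Half attributed | All attributed (extreme) | All AEs, both arms |
|---|---|---|---|
| 10% | 0.3% | 4.3% | 1.2% |
| 20% | 4.3% | 37% | 2.3% |
| 30% | 17% | 76% | 2.5% |
| 40% | 37% | 95% | 2.4% |

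The attributed count exceeds the nominal 5% only if the AE rate or the attributed share is fairly high. Counting all AEs in both arms stays at or below about 2.5% throughout.

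**The case against.** The strongest reply is that nothing has been lost. Section 10.1 requires every AE in every patient, relatedness is a field and not an entry filter, and section 11.3.3 omits the word related. Section 11.3.1 includes all randomised subjects in the analyses. On that reading an all-cause table by arm is already possible, and 5.3 is loose wording.

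Much of this stands. A reader might infer from 5.3 that control-arm AEs go unrecorded; sections 10.1, 10.1.1 and 9.2.3.1 contradict that. A reader might also infer that a planned randomised safety comparison is spoiled. No such comparison is expressly planned: 4.4 can be read as a description of the block, 11.1 states no safety hypothesis, and the only route to a test is the general sentence in 11.3.

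The size is also open to challenge. Section 3.5 names specific block complications and calls the risks extremely rare, so nothing in the documents supports attributing half of all events. At AE rates of 10% and 20% with half attributed, the false-positive chance is below 5%. A result of 0/20 would leave an exact 95% upper limit of 1 − 0.025^(1/20) = 16.8%, but that reflects the group size, and redefining the outcome would not change it.

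The reply does not settle which set of events is the outcome. Collecting data does not define what will be reported. Two sections give the same related-only definition, and the analysis section does not override it.

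**Conclusion.** The point holds as an inconsistency with a practical consequence. The safety outcome in 5.3 and 9.2.3 is limited to events that Group B cannot have and that an unblinded sponsor-investigator decides. Sections 10.1 and 9.2.3.1 collect all AEs, and 11.3.3 leaves open which set is analysed and whether by arm. Reported as defined, the outcome gives no randomised information on safety. That conclusion follows from the text and needs no assumed rate.

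The figures are illustrations. At 20 per arm, 5 versus 0 gives p = 0.047. With equal true rates and half of Group A's events attributed, the chance of p < 0.05 runs from 0.3% to 37% over assumed AE rates of 10% to 40%. They apply only if the attributed count is put through the general test rule. It would be too strong to conclude that the trial cannot yield an interpretable safety comparison, because the required data would support one. Safety is not the primary outcome, so this should be corrected but does not threaten the main result.

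**What to change.** In 5.3, 9.2.3 and 11.3.3, define the safety outcome as all AEs in both arms regardless of attributed cause, graded by CTCAE.

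- **Window.** Use one window for everyone, starting at randomisation or no later than the start of the anaesthetic procedures, and ending at the 4-week (out-patients) or 1-month (in-patients) visit. Starting at surgery would miss events at the injection itself, since the block comes before the operation. The sections disagree on whether the block precedes or follows the spinal anaesthesia and must be reconciled; either start point suggested here covers both orders.
- **Analysis.** In 11.3.3, state that AEs are tabulated by arm, with exact 95% confidence intervals.
- **Attribution.** Keep block-related events as a supporting descriptive listing for Group A, outside any between-arm test.

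The cost is wording in three sections and one additional table. No new visit or data item is needed, because 10.1 already requires the data.

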## **6. STUDY DESIGN**

### **6.1 General study design and justification of design**

This study is a randomized control single blind trial.

Patient will be randomized: Group A will undergo the pudendal nerve block under ultrasonographic control with injection of 10 mls of ropivacaine 0.75% before the spinal anaesthesia.

The population include patients with haemorrhoids (grade III and IV)

The study is single blind: an expert from the anaesthesiology team will perform the nerve block, the surgeon will be informed about the group of randomization. The nursing personnel (blinded) or the patient itself on specific formularies will evaluate the VAS scale at 6, 12, 24, 48 hours.

The comparator is no treatment

The method of randomization will be created by the CTU-EOC and the randomization will be performed by the authorized personnel (physician responsible for the study, the anaesthetist and the surgeons) of the participating centre via RedCap®. Only the physician responsible for the study, the anaesthetist and the surgeons will be informed about the treatment arm.

The expected duration of the study is 2 years, 100 patients.

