Measurements and procedures:	
Patients' clinical data and operative time will be collected
 
Patients selected will be randomized in two groups.
 
 
• Group A will undergo Milligan-Morgan hemorrhoidectomy under pudendal nerve block plus spinal anaesthesia
 
• Group B will undergo Milligan-Morgan hemorrhoidectomy under spinal anaesthesia
 
 
The randomization list will be created by the CTU-EOC and the randomization will be performed by the authorized personnel (physician responsible for the study, the anaesthetist and the surgeons) of the participating centre via RedCap®. Only the physician responsible for the study, the anaesthetist and the surgeons will be informed about the treatment arm.

	
After the operation all the patient will receive Metronidazole 500 mg x3 + Paracetamol 1 gr x4 + NSAID + opioids as needed for at least 48 hours. The postoperative pain will be evaluated at 6, 12, 24, 48 hours with VAS scale both as in-patients or out-patients on specific formularies. In-patients will be then controlled after 1 months, while out-patients after 1 and 4 weeks.
 
Results will be collected on specific printed Case report form. The Principal Investigator will preserve the sensitive data in his office in a closed cabinet key. Results will be then collected on a Redcap® electronic database. The access to the database will require username and password. Only the authorized personnel (physicians responsible for the study) will have the access rights and all changes on the database are trackable.

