
	
This procedure is usually a quite painful technique; thus, it is important to perform it after the spinal anaesthesia. It would be necessary to do it before the spinal anaesthesia just in case the pain would be associated to a nerve lesion. In this study the infiltration is not done on the nerve but in a muscular plane, thus is not needed the patient's sensibility.
 
The procedure will be performed at our institution by one of the three expert anaesthesiologists in the peripheral nerves' blockage. Those anaesthesiologists are:
 
 
• [name]. [name], Primario di Anestesia ORBV
 
• [name]. [name], Caposervizio Anestesia ORBV, board member of the Swiss Society of Loco-regional Anaesthesia
 
• [name]. [name], Caposervizio Anestesia e responsabile terapia del dolore ORBV
 

Control Intervention (if applicable):	None
Number of Participants with Rationale:	Based on previous studies we will expect a 33% reduction in VAS scale. To detect a clinically relevant difference between groups with a type I error of 0.05 and a power of 0.80 we determined a sample size of 18 subjects per group. Taken into account a possible drop out for different reasons of 10% we calculated the definitive sample size in 20 patients per group.
Study Duration:	According to the volume of the Milligan-Morgan hemorrhoidectomy performed every year in our centre, the estimated duration of the study is 2 years.
Study Schedule:	First-Participant-In planned: 01.01.2018 Last-Participant-Out planned: 31.12.2019
Investigator(s):	
[name] [name], Viceprimario Chirurgia ORBV, Bellinzona, [contact]
 
[name] [name], Caposervizio di Anestesia ORBV, Bellinzona, [contact]
 
[name] [name], Capoclinica Chirurgia ORBV, Bellinzona, [contact]
 
[name] [name], Medico Assistente Chirurgia ORBV, Bellinzona, [contact]

Study Centre(s):	Single-centre

[figure not shown]

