## **2.9 Early termination of the study**

The Sponsor-Investigator may terminate the study prematurely according to certain circumstances, for example:

- ethical concerns,
- insufficient participant recruitment,
- when the safety of the participants is doubtful or at risk, respectively,
- alterations in accepted clinical practice that make the continuation of a clinical trial unwise,
- early evidence of benefit or harm of the experimental intervention

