### **11.2 Determination of Sample Size**

Based on previous studies we will expect a 33% reduction in VAS scale. To detect a clinically relevant difference between groups with a type I error of 0.05 and a power of 0.80 we determined a sample size of 18 subjects per group. Taken into account a possible drop out for different reasons of 10% we calculated the definitive sample size in 20 patients per group.

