### **11.4 Handling of missing data and drop-outs**

In case of missing data, the patient will be dropped-out. 2 drop-outs each arm is planned

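### Section 6.1 gives 100 patients, but the sample-size calculation in 11.2 and the synopsis gives 20 per group in two groups, which is 40

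*Combined protocol and SAP*

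**What the plan says.** Section 6.1, after setting out the randomised, single-blind design and who performs the randomisation, closes with "The expected duration of the study is 2 years, 100 patients".

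Section 11.2 gives a different size. It states "we determined a sample size of 18 subjects per group", allows for 10% drop-out, and concludes "we calculated the definitive sample size in 20 patients per group". The synopsis carries the same paragraph under Number of Participants with Rationale. Under Measurements and procedures it says "Patients selected will be randomized in two groups", labelled A and B.

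Section 11.4 adds "2 drop-outs each arm is planned".

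On duration, the synopsis says "According to the volume of the Milligan-Morgan hemorrhoidectomy performed every year in our centre, the estimated duration of the study is 2 years" and attaches no patient number. Its schedule runs from 01.01.2018 to 31.12.2019. Section 2.9 lists "insufficient participant recruitment" among the example grounds on which the sponsor-investigator may stop the study early.

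**The concern.** Two groups of 20 make 40 patients, and section 6.1 says 100 for the same two years. The number to randomise is a basic design parameter, and here it has two values with no rule for choosing between them.

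Three things depend on it:

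- **The randomisation list.** The clinical trials unit has to build a list of a definite length.
- **The end of recruitment, and so the timing of the analysis.** Section 11.3.2 places the primary analysis at the end of the study. One reader could close enrolment at 40 and another at 100. The study physician, the anaesthetist and the surgeons know the allocation (6.1, 6.2.1), so whether to stop or continue should not be left for them to settle late in the trial.
- **The judgement of insufficient recruitment in 2.9.** The same 40 randomised patients would complete one target and be 40% of the other.

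If 100 were taken as the number to randomise, 60 people would enter the trial with no sample-size justification in the protocol.

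**Working it through.** **Inputs**

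- Evaluable patients per group: 18 (11.2 and synopsis)
- Drop-out: 10% (11.2 and synopsis)
- Final number per group: 20 (11.2 and synopsis)
- Number of groups: 2 (synopsis)
- Planned drop-outs per arm: 2 (11.4)
- Figure in the design section: 100 patients (6.1)

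**Step 1: reproduce the plan's own figure.** Inflating for drop-out, n = 18/(1 − 0.10) = 20 per group. The cruder form, 18 × 1.10 = 19.8, also rounds up to 20. The stated 20 per group is reproduced either way.

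**Step 2: total.** 2 × 20 = 40 randomised, of whom 2 × 18 = 36 are evaluable.

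**Step 3: check against 11.4.** 20 − 18 = 2 drop-outs per arm, and 10% of 20 = 2. Section 11.4 agrees with 20 per arm. If 100 were randomised equally, each arm would have 50. At 10% the drop-outs would then be 5 per arm, and 2 of 50 is only 4%. Section 11.4 therefore does not fit 100.

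**Step 4: can 100 be reached from the stated inputs?** Going from 36 evaluable patients to 100 randomised needs a drop-out of 1 − 36/100 = 64%, against the stated 10%. It cannot.

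**Step 5: size of the gap.** 100 − 40 = 60 patients; 100/40 = 2.5; 40/100 = 40%.

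**Step 6: what the two sizes mean statistically.** With two-sided α = 0.05 and 80% power, 18 per group corresponds to a standardised difference of (1.960 + 0.842) × √(2/18) = 0.934 (normal approximation; 0.961 with a t-test). At a difference of 0.934, power is 80% with 18 per group, 84% with 20 and 99.7% with 50. With 50 per group, 80% power would be reached at (1.960 + 0.842) × √(2/50) = 0.56. The two figures therefore describe trials aimed at clearly different effects.

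**Limit of the check.** The 18 itself cannot be reproduced. Section 11.2 gives a 33% reduction in VAS but no control mean and no SD. Assuming a control mean between 3 and 7, 18 per group implies an SD of about 1.06 to 2.47 (normal approximation). Assuming a control mean of 5, the number per group is 13, 24, 37 or 52 for an SD of 1.5, 2, 2.5 or 3. So 40 is the total consistent with the text, not a verified requirement.

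**The case against.** The strongest reply is that there is little real ambiguity. The section whose job is to set the size calls 20 per group definitive, the synopsis repeats it, and 11.4 agrees. Against these stands one loose clause whose subject is duration and which does not say enrolled or randomised. The synopsis ties the two years to the centre's surgical volume, so 100 may be the expected pool of cases. On that reading the defect is a missing label.

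Some further points are fair:

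- Nothing in 11.2's drop-out step is miscalculated; the fault is a conflict between sections.
- Section 2.9 is permissive and sets no threshold, so the 40% figure only illustrates the problem.
- The 5 drop-outs per arm arise only if 100 is first assumed to be the number randomised.
- The synopsis dates bound the study in calendar time, though they do not fix the number.
- Under 11.2's own assumptions, a larger trial would have more power, not less.

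These points make 40 the likely intention and limit the consequences. They do not remove the conflict. No passage calls 100 a case pool, a screening number or a revised target, and it sits in the design section just after the randomisation procedure, where a reader would naturally take it as enrolment.

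**Conclusion.** The concern holds. Section 6.1 conflicts with 11.2, the synopsis and 11.4: 100 patients against 40, a difference of 60, or 2.5-fold. The total of 40 rests on two groups of equal size, as the per-group figure implies. It is the only total with a derivation behind it, and 6.1 is probably the figure in error. The documents do not settle whether 100 is a slip, an unlabelled case volume or a changed target. The conclusion does not depend on whether 18 per group is itself well founded, which the missing control mean and SD leave open.

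**What to change.** State one number to randomise, and print the total as well as the per-group figure in 6.1, 11.2 and the synopsis.

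- **If the 11.2 calculation stands:** replace the 100 in 6.1 with 40 patients (20 per group). This is a one-line correction with no extra patients and no change of design.
- **If 100 is a case-volume or screening figure:** label it so in 6.1 and still give 40 as the number to randomise. The cost is again one line.
- **If 100 randomised is intended:** replace the calculation in 11.2 and the synopsis, stating the control mean and SD used, and revise the drop-out count in 11.4. This means 60 more patients than 11.2 supports.

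Any of these changes needs sponsor and ethics committee approval under section 2.3. The randomisation list should be checked against the confirmed total.
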